4.3 PE parameters for secondary analyses of prevention efficacy

Secondary analyses assess PE parameters for the mAb dose groups separately. Let PE10 be the overall PE of the 10 mg/kg mAb group and let PE30 be the overall PE of the 30 mg/kg mAb group, defined as

 $PE10 = [1 - Cumul. incid. ratio (mAb-10 mg/kg grp/control) of HIV-1 Dx by 80 Wks] \times 100\%$

and

 $PE30 = [1 - Cumul. incid. ratio (mAb-30 mg/kg grp/control) of HIV-1 Dx by 80 Wks] \times 100\%$.

Secondary analyses test the null hypotheses

H0: PE10 = 0% versus the alternative hypothesis H1: PE10 \neq 0%

and

H0: PE30 = 0% versus the alternative hypothesis H1: PE30 \neq 0%

using 2-sided alpha = 0.05 level tests. Both unadjusted p-values and Holm-Bonferroni p-values will be reported for each of the individual dose versus placebo group analyses.

In addition, the following secondary analyses of PE are conducted:

• Assess a dose-response effect by testing the null hypothesis

H0: Cumul. HIV-1 incidence by 80 Wks equal in the 3 groups versus H1: $0\% \le PE10 \le PE30$ with at least one strict inequality

- Test the complete null hypothesis that the HIV-1 incidence is the same in the three treatment groups versus the alternative hypothesis that there are some differences
- Test for different HIV-1 incidence between the two mAb groups, where a finding of PE30 significantly greater than PE10 would demonstrate that assignment to a higher mAb dose level causes higher PE

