## **8 Statistical Analysis of Prevention Efficacy**

Except where specified, all prevention efficacy endpoint analyses are performed in the MITT cohort. All analyses only use samples and data collected prior to study unblinding. Unless either of the trials is stopped prematurely, the common data cut date for the final prevention

efficacy analysis in both trials is set to be May 1, 2020, which includes more than 80 weeks of follow-up for the last enrolled participant in each trial (80 weeks after the last enrollment falls on April 2, 2020 in HVTN 703/HPTN 081 and April 17, 2020 in HVTN 704/HPTN 085).

All analyses specified in Sections 8.1, 8.2, and 8.3 are conducted in each AMP trial separately, as well as pooled over the two AMP trials. The statistical methods are the same, except the pooled analyses additionally stratify for study. For cumulative incidence-based pooled analyses, stratification is performed by estimating the cumulative hazard separately within each combination of study and treatment group (requiring at least 10 total primary HIV-1 infection endpoints within each combination of study and treatment group), and, for Cox model-based pooled analyses, stratification is performed by using a separate baseline hazard for each study (requiring at least 10 total primary HIV-1 infection endpoints within each study to include the trial as a stratification covariate).

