## 8.2 Secondary Analyses of Prevention Efficacy

Secondary analyses assess PE parameters for the mAb dose groups separately. Let PE10 be the overall prevention efficacy of the 10 mg/kg mAb group and let PE30 be the overall prevention efficacy of the 30 mg/kg mAb group, defined as

$$PE10 = \left\{ 1 - \text{cumulative incidence ratio (mAb 10 mg/kg group/control group)} \right. \\ \left. \text{of the primary efficacy endpoint by 80 weeks} \right\} \times 100\%,$$

and

$$PE30 = \left\{ 1 - \text{cumulative incidence ratio (mAb 30 mg/kg group/control group)} \right. \\ \left. \text{of the primary efficacy endpoint by 80 weeks} \right\} \times 100\%.$$

The PE10 and PE30 parameters will be assessed using the same estimation method as described in Section 8.1.

We will conduct secondary analyses to test the null hypotheses

$$H_0 : PE10 = 0\% \text{ versus the alternative hypothesis } H_1 : PE10 \neq 0\%$$

and

$$H_0 : PE30 = 0\% \text{ versus the alternative hypothesis } H_1 : PE30 \neq 0\%$$

using 2-sided  $\alpha = 0.05$  level Wald tests described in Section 8.1. Both unadjusted p-values and Holm–Bonferroni-adjusted p-values (Holm, 1979) will be reported for each of the individual dose versus control group analyses.

In addition, the following secondary analyses of PE will be conducted:

- (i) Assess a dose-response effect by testing the null hypothesis

$$H_0 : \text{cumulative HIV-1 incidence by 80 weeks is equal in the three study groups versus} \\ H_1 : 0\% \leq PE10 \leq PE30 \text{ with at least one strict inequality.}$$

- (ii) Test the null hypothesis that the cumulative HIV-1 incidence by 80 weeks is equal in the three study groups versus the alternative hypothesis that there are some differences.

- (iii) Test the null hypothesis that the cumulative HIV-1 incidence by 80 weeks is equal in the two mAb groups versus the alternative hypothesis that PE30 is greater than PE10, which would demonstrate that assignment to a higher mAb dose level causes higher PE.

Hypotheses (i)–(iii) will be tested using cumulative hazard function based Wald tests. Define the Wald test statistic

$$W_{i,j} = \frac{\log \widehat{\Lambda}_i(80 \text{ weeks}) - \log \widehat{\Lambda}_j(80 \text{ weeks})}{\sqrt{\widehat{\text{var}}\{\log \widehat{\Lambda}_i(80 \text{ weeks})\} + \widehat{\text{var}}\{\log \widehat{\Lambda}_j(80 \text{ weeks})\}}},$$

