where  $\widehat{\Lambda}(\cdot)$  is the Nelson-Aalen estimator and  $i, j \in \{c, 10, 30\}$ ,  $i \neq j$ , represent the control, 10 mg/kg mAb, and 30 mg/kg mAb group, respectively. The test statistic considers the estimated variance of the Nelson-Aalen estimator proposed in Aalen (1978).

The alternative hypothesis in (i) is equivalent to  $\widetilde{H}_1 : \Lambda_c(t_0) \geq \Lambda_{10}(t_0) \geq \Lambda_{30}(t_0)$ ,  $t_0 = 80$  weeks, with at least one strict inequality, and therefore the test of (i) will reject  $H_0$  if both  $W_{c,10} \geq \Phi^{-1}(0.975)$  and  $W_{10,30} \geq \Phi^{-1}(0.975)$ , where  $\Phi^{-1}$  is the quantile function of the standard normal distribution. The test of (ii) will reject  $H_0$  if at least one of  $|W_{c,10}| \geq \Phi^{-1}(0.975)$  and  $|W_{10,30}| \geq \Phi^{-1}(0.975)$  holds. The test of (iii) will reject  $H_0$  if  $W_{10,30} \geq \Phi^{-1}(0.975)$ .

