### **8.3.2 Additional Analyses Included in the Final Analysis**

All of the primary and secondary analyses of overall prevention efficacy specified in Sections 8.1 and 8.2 will be repeated for the endpoint HIV-1 infection with sensitivity type Sensitive or Moderately Sensitive according to the definitions above. The statistical methods are the same, except cumulative incidence estimators are replaced with cause-specific cumulative incidence estimators and Cox model analyses right-censor primary HIV-1 infection endpoints of a different sensitivity type.

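### SAP 8.2 test (ii) of equal incidence in three groups combines two unadjusted 5% tests: about 9% false positives, and less power than a 2-df Wald test when PE10 lies between 0 and PE30

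*SAP*

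**What the plan says.** Hypothesis (ii) in SAP 8.2 is "Test the null hypothesis that the cumulative HIV-1 incidence by 80 weeks is equal in the three study groups", against the alternative that some differ. Protocol 4.3 lists the same item ("Test the complete null hypothesis that the HIV-1 incidence is the same in the three treatment groups") but gives no rejection rule.

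The SAP says that hypotheses (i) to (iii) "will be tested using cumulative hazard function based Wald tests". W(i,j) is the difference of log Nelson-Aalen cumulative hazards at 80 weeks divided by its standard error. For (ii) the rule is "The test of (ii) will reject $H_0$ if at least one of" |W(c,10)| and |W(10,30)| is at or above the 0.975 standard normal quantile, 1.96. W(c,30) is not used.

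On level and multiplicity:
- Neither document states a level for (ii). The neighbouring PE10 and PE30 tests are done "using 2-sided alpha = 0.05 level tests" (Protocol 4.3).
- Unadjusted and Holm-Bonferroni p-values "will be reported for each of the individual dose versus control group analyses". That adjustment does not extend to (ii).

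The rule is used more than once. SAP Section 8 says the analyses "are conducted in each AMP trial separately, as well as pooled over the two AMP trials". SAP 8.3.2 adds, for the neutralization-sensitive endpoint: "All of the primary and secondary analyses of overall prevention efficacy specified in Sections 8.1 and 8.2 will be repeated".

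**The concern.** Rejecting when either of two 5% tests rejects gives an overall level above 5% unless the cut-off is raised, and it is not raised here. A reader who sees the 0.975 quantile will take (ii) to be a 5% test.

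The second issue is which contrasts are used. The two adjacent dose steps together span the null hypothesis, so the choice is coherent. But when PE10 is intermediate, the full effect is split across the two steps, and the control versus 30 mg/kg comparison that would show it whole is not in the rule. The report could then state that no difference was found among the three groups, next to a significant PE30.

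**Working it through.** **Inputs.** 900 per arm (Protocol 4.6.2). 3% annual control incidence, 10% annual dropout and 80 weeks of follow-up (Protocol 4.6.1). 1.65% as the low-incidence case (Protocol 4.6.1 and 4.6.3). Statistic and variance as in SAP 8.2. Infection and dropout times are exponential, event times are exact, and there is no interim stopping.

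**Reproducing the plan's own figures.** The documents give no size or power for (ii), so the model was checked on what they do give.
- Control events: 900 × 0.03 × (1 − exp(−0.13 × 80/52))/0.13 = 37.6. Pooled mAb events at PE = 60%: 1800 × 0.012 × (1 − exp(−0.112 × 80/52))/0.112 = 30.5. Protocol 4.6.4 states 37 and 30.
- Table 4-4, power to detect PE10 different from PE30, in row order. Stated: 58.3, 39.5, 21.6, 83.7, 69.4, 91.5, 90.8, 77.0%. Simulated (8,000 trials each): 57.9, 38.5, 21.0, 84.0, 68.7, 91.0, 91.3, 77.5%. All are within 2 points.

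**Size.** W(c,10) and W(10,30) share the 10 mg/kg arm with opposite signs. With equal variances V under the null, their correlation is −V/(2V) = −0.5. Then:
- 1 − P(|Z1| < 1.96 and |Z2| < 1.96) at correlation −0.5 = 0.0907.
- Simulated (20,000 trials): 8.6% for the SAP rule, 4.5% for a 2-df Wald test. At 1.65% incidence: 8.5% and 4.4%.
- Adding the third contrast, also unadjusted, gives 12.2%.
- The two-contrast rule needs a cut-off of 2.21 for 5% size.

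**Why power is lost when PE10 is intermediate.** At (PE10, PE30) = (30, 60) the expected events are 37.6, 26.5 and 15.3. With the variance of each log cumulative hazard close to 1/events, the expected statistics are:
- control vs 10 mg/kg: ln(1/0.7)/√(1/37.6 + 1/26.5) = 0.357/0.254 = 1.41
- 10 vs 30 mg/kg: ln(0.7/0.4)/√(1/26.5 + 1/15.3) = 0.560/0.321 = 1.74
- control vs 30 mg/kg (not in the rule): ln(1/0.4)/√(1/37.6 + 1/15.3) = 0.916/0.303 = 3.02

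The normal approximation then gives 65% power for the SAP rule and 78% for the 2-df test (critical value 5.99).

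**Simulated power** (20,000 trials per row, Monte Carlo standard error at most 0.35 points):

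| PE10, PE30 (%) | SAP rule | 2-df Wald | SAP contrasts, cut-off 2.21 |
|---|---|---|---|
| 20, 60 | 71% | 82% | – |
| 30, 60 | 64% | 80% | 49% |
| 40, 60 | 66% | 82% | – |
| 50, 70 | 85% | 95% | – |
| 60, 60 | 90% | 92% | – |
| 0, 60 | 90% | 90% | 83% |
| 0, 50 | 73% | 71% | 62% |
| 30, 30 | 32% | 30% | 22% |
| 60, 0 | 96% | 90% | 93% |
| 30, 60 at 1.65% incidence | 39% | 50% | – |

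**Disagreement with PE30.** At (30, 60), (ii) is non-significant while control vs 30 mg/kg is significant in 26% of trials using the unadjusted p-value, and in 21% using the Holm-adjusted one. With the 2-df test the unadjusted figure falls to about 9%.

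**The case against.** The strongest reply is that little depends on (ii). It is one of several secondary tests, and no stopping rule, gatekeeping step or primary claim uses it. The Holm-adjusted PE10 and PE30 p-values already test the same null, with simulated size 4.0% and power 82% at (30, 60). The 2-df test rejects where the Holm pair does not in only 1.5% of trials at (30, 60), 1.6% at (40, 60) and 3.3% at (20, 60). This stands and limits the harm on the power side. It does not correct (ii), which is reported in its own right. Under the null, (ii) rejects without the Holm pair in about 5.7% of trials.

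Three further points have weight:
- The 5% target is inferred, so no stated level is contradicted. But nothing in either document suggests that a 9% level was intended.
- Adjacent dose steps are a legitimate choice that matches tests (i) and (iii), and the SAP rule equals or beats the 2-df test in some flat or non-monotone cases. Most of that comes from the inflated size. At a cut-off of 2.21 it keeps a lead only at (60, 0), the reverse of the ordering in hypothesis (i).
- Any omnibus test can disagree with one of its contrasts. The 2-df test reduces the disagreement by about two-thirds but does not remove it.

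The no-interim-stopping assumption does not rescue the rule: with an approximate version of the non-efficacy and high-efficacy monitoring, its size was 9.5%.

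**Conclusion.** The concern holds. The unadjusted cut-off is the defect: as written, (ii) has a type I error of about 9% against an apparent 5%. The power loss supports replacing the rule rather than only raising its cut-off. With PE10 intermediate, the simulated loss at 3% incidence is 10 to 16 points, and 11 points at (30, 60) with 1.65% incidence.

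The gap is not uniform. At (20, 40) the normal approximation gives 32% against 39% at 3% incidence, and 22.0% against 23.2% at 1.65%. There is no loss at PE10 = 0.

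The power figures rest on the protocol's design assumptions. The asymptotic size rests only on the shared arm and roughly equal variances under the null. Size and power were not computed for the trial-pooled analysis or for the sensitive-virus endpoint, where SAP 8.3.2 substitutes cause-specific estimators, so these numbers should not be carried over to them. This should be fixed, but it does not threaten the trial's primary conclusion.

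**What to change.** Replace the rejection rule for (ii) in SAP 8.2 with a single 2-df Wald chi-square test of log Λc = log Λ10 = log Λ30 at 80 weeks, and state the level as 0.05. With L_g the log Nelson-Aalen estimate and w_g the inverse of its estimated variance, the statistic is Q = Σ w_g (L_g − L̄)², where L̄ is the w-weighted mean. Reject if Q ≥ 5.99. Make the matching change wherever (ii) is repeated, in the trial-pooled and sensitive-virus analyses.

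Two simpler repairs should be avoided. Adding control versus 30 mg/kg as a third unadjusted contrast raises the size to 12.2%. Keeping the two contrasts and raising the cut-off to 2.21 restores 5% size, but power at (30, 60) drops to 49%.

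The cost is one sentence of SAP wording and one line of code, with no new data. The downside is slightly lower power in some flat or non-monotone cases: 32% to 30% at (30, 30) and 96% to 90% at (60, 0).

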4.2 PE parameter for the primary analysis of prevention efficacy

Let PE denote the overall PE of the 10 mg/kg and 30 mg/kg mAb groups pooled together compared to the control group. This PE parameter is defined as

 $PE = [1 - Cumul. incid. ratio (pooled mAb grp/control) of HIV-1 Dx by 80 Wks] \times 100\%$

where the cumulative incidence ratio is the probability of HIV-1 diagnosis by the Week 80 visit for participants assigned to receive the mAb divided by the probability of HIV-1 diagnosis by the Week 80 visit for participants assigned to receive control. PE is the target parameter for the primary analysis of overall PE.

The primary analysis tests the null hypothesis

H0: PE = 0% versus the alternative hypothesis H1: $PE \neq 0\%$

using a 2-sided alpha = 0.05 level test that accounts for sequential monitoring for potential harm, non-efficacy, and high efficacy.

4.2.1 Rationale for the PE parameter that measures prevention efficacy averaging over participant subgroups that access different elements of the HIV-1 prevention package

The primary PE parameter measures the efficacy of VRC01 averaging over the 10 mg/kg and 30 mg/kg subgroups, in the population-based context of study participants with different risk characteristics including host genetics, HIV-1 risk taking behaviors, and

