4.6 Sample size calculations for testing for overall PE (Primary objective 2)

The trial is designed to have 90% power to test

H0: $PE \le 0\%$ versus the alternative hypothesis H1: PE > 0%

if the level of overall pooled PE is 60% (with a 1-sided 0.025 α -level test); the design fits the paradigm of an intermediate-sized phase 2b screening efficacy trial proposed for HIV-1 vaccine efficacy trials by Rida, Fleming et al [117].

The sample size calculations are based on the power of a 1-sided 0.025-level Wald test for comparing log-transformed cumulative incidences of HIV-1 infection by the Week 80 visit between randomized groups, in the presence of the sequential monitoring described below. Power is computed based on simulating 10,000 efficacy trials under assumptions described below using the R package seqDesign.

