4.6.1 Assumptions of the sample size calculations including sequential monitoring for PE

The following assumptions are made for the sample size calculations:

- 10% annual dropout incidence in each of the three study groups
- 32 month uniform accrual with halved accrual during the first three months (approximating current accrual projections)
- visits every 4 weeks for HIV-1 diagnostic tests through Week 80 and HIV-1 status at Week 80 is known
- 3% annual HIV-1 incidence in the control group

- For each of the mAb treatment groups, average PE versus control within an 8-week infusion interval is assumed to be the same for each of the 10 infusion intervals
- Sequential monitoring of the mAb groups versus control to stop early for:
 - Potential harm [Establish that PE (pooled over the mAb groups) < 0% based on a 2-sided monitoring adjusted 90% CI lying below 0%]
 - Non-efficacy [Establish that PE (pooled over the mAb groups) $\leq 40\%$ based on a 2-sided 95% nominal CI lying below 40%]
 - High efficacy [Establish that PE (pooled over the mAb groups) > 70% based on a 2-sided 95% nominal CI lying above 70%]

With the exception of the potential harm monitoring, the sequential monitoring of PE does not use critical values adjusted for the number of analyses. Examination of the design operating characteristics (reported in the figures and tables below) was used to ensure that this approach provides a fitting trade-off of the control of false negative and false positive error rates.

Justification for the incidence assumptions is provided in Section 4.6.6.

We also show power calculations allowing for lower levels of HIV-1 incidence or higher levels of dropout. In particular, we show power calculations assuming 1.65% annual HIV-1 incidence in the control group, which would account for lower than expected incidence rates due to increased PrEP usage. Similarly, power calculations based on 15% annual dropout incidence are also considered.

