As a supportive analysis of the hypotheses in (2), targeted minimum loss-based estimation (TMLE) may be used to estimate cumulative incidences of the primary efficacy endpoint over time for the pooled mAb arm and the control arm. Iterative mean-based TMLE is used for this analysis as described in Benkeser, Carone, and Gilbert (2016). The Super Learner (van der Laan, Polley, and Hubbard, 2007) is used to generate initial estimates of the conditional censoring distribution and the iterated conditional means. The Super Learner library includes both parametric and nonparametric algorithms: generalized linear models, generalized additive models with 2 or 3 degrees of freedom, a regression tree (Breiman et al., 1984), and a random forest (Breiman, 2001) (specified in Table 2). Each method considers adjustment for baseline demographic covariates, the baseline behavioral risk score built via supervised learning as described in Section 8.6, and two-way interactions of these terms. The baseline demographics to adjust for are country (if there are at least 10 total primary HIV-1 infection endpoints in a country – otherwise categories are collapsed) and AMP study (for analyses that pool the two AMP trials). The candidate algorithms in the Super Learner library consider various adjustments for time, as shown in Table 2. TMLE analyses will produce plots of estimated cumulative PE on both the multiplicative mAb efficacy and additive-difference scales, as done for the primary analyses. The TMLE analyses will be implemented using the *survtmle* R package available at CRAN.

PE parameters will be estimated by 1 minus the ratio (pooled mAb groups/control group) of these tMLE estimators. Influence-curve based variance estimators of each cumulative incidence is used, and the delta method applied to obtain the variance estimator of the log

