In each AMP trial, the estimation will be carried out separately in the control (restricted and enriched for HVTN 703/HPTN 081) and pooled VRC01 groups, i.e., the estimators will be trained separately on data from participants in the control and pooled VRC01 groups (estimation in individual VRC01 dose groups is not considered due to potential convergence failures and limited precision). The best-performing estimator  $\widehat{\psi}_z$  for  $\psi_{0,z}$  will also be identified independently for each  $z \in \{\text{control, pooled VRC01}\}$  in each trial. For the control-group prediction in HVTN 703/HPTN 081, the candidate estimators including the superlearner trained on the restricted control-group data and the candidate estimators including the superlearner trained on the enriched control-group data will be all evaluated together for prediction accuracy, identifying a single best-performing estimator across both the restricted and enriched control-group data sets. For the  $i$ -th enrolled participant with a baseline covariate vector  $W_i$ , the predicted HIV-1 risk score is then defined as the ordered pair  $\left(\widehat{\psi}_{\text{control}}(W_i), \widehat{\psi}_{\text{pooledVRC01}}(W_i)\right)$  of the best-performing estimators.

In more detail, within each combination of trial and treatment stratum, a set of candidate estimators  $\{\widehat{\psi}_1, \dots, \widehat{\psi}_K\}$ , specified in Table 5 in the KwaZulu-Natal risk prediction SAP, and a superlearner estimator  $\widehat{\psi}_{SL}$  for  $\psi_{0,z}$  will first be constructed following Algorithm 1 below. The best-performing estimator  $\widehat{\psi}_z$  is defined as an estimator from the set  $\{\widehat{\psi}_1, \dots, \widehat{\psi}_K, \widehat{\psi}_{SL}\}$  with maximal cross-validated AUC in the treatment stratum  $Z = z$  (see Algorithm 2 below). Following identification of the best-performing estimator in each treatment stratum, we will compute the estimated/predicted HIV-1 risk score for all enrolled participants.

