For the HVTN 703/HPTN 081 enriched control-group candidate estimators,  $W$  will consist of the baseline demographic characteristics specified above and the questionnaire data from the HVTN 702 behavioral risk assessment. The HVTN 702 behavioral risk assessment consists of 23 questions which, like the HVTN 703/HPTN 081 behavioral risk survey, aim to assess risk of HIV infection. Some questions in the HVTN 702 assessment correspond, in part, to questions in the full HVTN 703/HPTN 081 survey but are structured differently. Questions between the two assessments which capture similar information (e.g., number of sex partners) will be consolidated into a single feature where possible. Survey items in the HVTN 702 survey that were not included in the full HVTN 703/HPTN 081 survey (e.g., age at sexual debut) will be multiply imputed using the missForest method. No other covariates from the full HVTN 703/HPTN 081 survey will be used in fitting the enriched control-group candidate estimators. Note that imputation of the enriched data set will be performed separately from the imputation of the restricted HVTN 703/HPTN 081 survey described above. Since this analysis considers a large fraction of imputed responses, another set of candidate estimators will be fit using only the questions that are shared between the HVTN 702 and the full HVTN 703/HPTN 081 surveys. The best-fitting estimator will be identified from the pooled set of estimators based on the complete/imputed and the restricted/enriched control-group data sets in HVTN 703/HPTN 081.

Internal validation of  $\widehat{\psi}_z(W)$  (see Algorithm 2 below) will be based on cross-validated predictions using only data from the AMP trials (with no additional external training set to train the learners). External validation will not be performed. Computation time of `survtmle` scales with the resolution of  $T$ . To limit computation time, person-time will be rounded up to the nearest month.

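### The supportive TMLE should adjust for a cross-fitted risk score and name the component used; as planned, each component is in-sample for one arm and out-of-sample for the other

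*SAP*

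**What the plan says.** SAP 8.2 describes a supportive TMLE of the week-80 cumulative incidences. Its models adjust for baseline demographics and "the baseline behavioral risk score built via supervised learning as described in Section 8.6". Table 2 calls this score B and enters it in the outcome models both as a main effect and crossed with treatment (Z×B). The SAP makes this analysis optional; Protocol 4.13.4.1 commits to it.

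SAP 8.6 defines the score. Its outcome is time to the primary endpoint. Learners are trained separately in the control and pooled VRC01 arms, and the candidate or super learner with the highest cross-validated AUC is kept for each arm. After that, "we will compute the estimated/predicted HIV-1 risk score for all enrolled participants", so each person has an ordered pair: a control-trained value and a VRC01-trained value. In Algorithm 1, step 13 fits each learner on the whole arm, and the output is predictions for those same participants. Cross-validation sets the super learner weights and supplies the AUC: internal validation "will be based on cross-validated predictions using only data from the AMP trials". No out-of-fold score is specified for use as B, and neither SAP 8.2 nor Table 2 says which member of the pair B is.

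**The concern.** Covariate adjustment in a randomised comparison is safe when the covariate is fixed at baseline and so independent of assignment. A score fitted to one arm's outcomes and then read off the same fit for everyone does not meet that condition. In the training arm it carries part of each participant's own outcome; in the other arm it does not. The two arms then differ in B for a reason unrelated to risk, and standardising over both arms turns that difference into an apparent effect.

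TMLE's own Super Learner gives no protection: B is computed before its folds are drawn, so the held-out folds already contain the outcome through B and favour models that include it. At stake is a covariate-adjusted estimate with Wald intervals and p-values, reported beside the primary result.

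**Working it through.** **Inputs.** Protocol 4.6.1: "3% annual HIV-1 incidence in the control group" and "10% annual dropout incidence in each of the three study groups". Protocol Table 4-2: 900 control, 1800 pooled mAb. Follow-up is 80/52 years. Power is "based on the power of a 1-sided 0.025-level Wald test" (Protocol 4.6), while the primary analysis is specified "using a 2-sided alpha = 0.05 level test that accounts for sequential monitoring" (Protocol 4.2). The design alternative is PE 60%.

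**Step 1: reproduce the design.** Expected events = nλ/(λ+d) × [1 − exp(−(λ+d)×80/52)].

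- Control: 900 × 0.03/0.13 × (1 − e^−0.200) = 37.65 (Protocol 4.6.4: 37).
- mAb at PE 60%: 1800 × 0.012/0.112 × (1 − e^−0.1723) = 30.53 (Protocol: 30).
- Power: SE = √(1/37.65 + 1/30.53) = 0.2436; 0.916/0.2436 − 1.96 = 1.80; Φ(1.80) = 96.4% (Table 4-1: 96.0%).

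The simulated risks are therefore 37.65/900 = 4.18% and, at PE 60%, 30.53/1800 = 1.70%.

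**Step 2: the limit of complete overfitting.** Suppose the control-trained score isolates control cases perfectly and no mAb participant receives a similar value. The outcome model then predicts almost no control-arm risk for the 1800 mAb participants, and standardised control incidence falls to 900/2700 = 1/3 of its value. With RR the true risk ratio:

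- Control component: PE = 1 − 3RR, or -200% at RR 1 and -20% at RR 0.4.
- VRC01 component: standardised mAb incidence falls to 1800/2700 = 2/3, so PE = 1 − (2/3)RR, or +33% and +73%.
- Both components: PE = 1 − 2RR, or -100% and +20%.

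**Step 3: simulation.** 900/1800 participants, binary endpoint by week 80, 20 baseline covariates (the number kept by the SAP's random-forest screen). The score was fitted by arm and predicted as in Algorithm 1. TMLE chose among Z, Z+B and Z×B by 10-fold cross-validation, with arm-specific targeting and influence-curve standard errors. Signal was moderate. Median adjusted PE, with rejection at PE 0 and coverage at PE 60% in brackets where available:

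| Score learner | B | True PE 0 | True PE 60% |
|---|---|---|---|
| Logistic (150 replicates) | fixed component | -0.3% to -1.6% (5–6%) | 58–59% |
| Lasso (40) | control | -4.0% (5%) | 56.4% (92.5%) |
| Lasso (40) | VRC01 | -4.2% (2.5%) | 57.1% (92.5%) |
| Forest, leaf 15 (30) | control | -28% (37%) | 44% (60%) |
| Forest, leaf 15 (30) | VRC01 | +24% (40%) | 70.5% (73%) |
| Forest, leaf 15 (30) | both | +12% (13%) | 60% (93%) |
| Forest, leaf 1 (30) | control | -213% (100%) | -18% (0%) |
| Forest, leaf 1 (30) | VRC01 | +44% (83%) | 76% (30%) |
| Forest, leaf 1 (30) | both | -81% (90%) | 28% (33%) |

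Unadjusted medians in the same replicates were -5.0% and 56.1% (lasso), -4.6% and 61.5% (leaf 15) and about 6% and 61.8% (leaf 1), so the lasso rows show no shift. With no true signal (20 replicates), leaf 1 gave -200%, +35% and -100% at PE 0, in line with step 2. The control score's AUC was 1.00 in-sample and 0.56 out-of-fold for leaf 1, 0.99 and 0.58 for leaf 15, and 0.73 and 0.59 for lasso.

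A third reading of B, each participant's own-arm prediction, makes B nearly a copy of assignment: at true PE 60% the median was 36% even with logistic and 0% with leaf 1.

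**Step 4: cross-fitting.** With 5-fold cross-fitted scores, the leaf-1 forest gave median PE of 4% (control component) and 3% (both) at PE 0, with 6.7% rejection (2 of 30), and 61.8% at PE 60% with 96.7% coverage. Leaf 15 gave -6% and 62%, in line with its unadjusted medians.

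**The case against.** The strongest reply is that the size rests on a learner the documents do not name. The candidate list is in a separate risk-prediction SAP. SAP 8.6 mentions a survival forest only as a screening method. The tree and forest in SAP 8.2 belong to the TMLE library rather than the score, and Table 2 lists neither. The score is also chosen by cross-validated AUC, which does not reward in-sample fit. In a separate check with three candidates (forest, logistic, lasso; no super learner), that rule chose the forest in 20% of 45 runs with a modest linear signal and 45% of 40 runs with none. These are not probabilities for this trial, but they show that selection makes the problem less likely without excluding it. SAP 8.6 also allows for data-adaptive learners in a footnote to Algorithm 1.

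Scope is limited too. Cox, log-rank and Gehan-Wilcoxon analyses, none using B, accompany the primary estimate, so a discordant TMLE would be noticed.

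A reader might infer that the TMLE as written is bound to be severely biased, or that the primary result is at risk. The documents support neither. With a logistic or lasso score and a fixed component the bias is negligible, and the primary Nelson-Aalen analysis does not use the score. What stands is that the plan permits an outcome-contaminated covariate, has no guard against it, and leaves open the choice that sets the direction of any bias.

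**Conclusion.** The point holds as a cheap improvement to the supportive TMLE only. The same outcomes, arm-specific training and full-arm prediction are all documented. The consequence runs from none (logistic or lasso, fixed component) to large (forest), and its sign depends on which component is B.

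The forest figures are conditional on a forest being selected. With 30 replicates each, rejection rates carry up to about ±18 points of Monte Carlo error (1.96 × √(0.25/30)); the leaf-1 shifts far exceed that, and their size agrees with the allocation arithmetic. The simulation assumes 20 covariates, an out-of-fold AUC of about 0.5–0.6, no censoring, constant treatment probability and no demographic covariates. It fixes one learner per run and does not reproduce the SAP's AUC selection or super learner.

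**What to change.** In SAP 8.2 and 8.6, state which component or components of the score serve as B, and define B by cross-fitted predictions. For participants in the training arm, use the out-of-fold predictions that Algorithm 2 already forms. For participants in the other arm, average the fold-specific fits; Algorithm 2 does not currently produce these, so they must be added.

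The cost is a short text change, a small amount of extra computation for the other-arm predictions, and a slightly less sharp score. No new data are needed and the primary analysis is unchanged.
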